9.2.8 Early Termination Visit

Subjects who decide not to continue with the study procedures or who are withdrawn from the study should complete an early termination visit.

Procedures at the early termination visit are the same as mentioned in Section 9.2.3 for the Month 12 visit, with the addition of a neurological and a physical examination. Subjects will be prescribed an appropriate commercial LD/DDI dose as determined by the investigator and will return the infusion pump system to the site.

Early termination visits should also be performed for any subject who prematurely discontinues from the optional treatment extension period and the optional long-term extension period. For early termination visits during the extension periods, safety laboratory tests (blood chemistry, hematology, and dipstick urinalysis) and 12-lead ECG recordings should be done at the investigator's discretion and associated data will be analysed locally (i.e., not at a central lab/by a central reader).

Reasons for withdrawal of the subject before completion of the study must be stated in the eCRF and in the site source documentation for all study subjects who were enrolled in the study. The sponsor should be informed of all subjects who are withdrawn due to AEs.

An in-person safety follow-up visit should take place 1, 2 and 3 months after the actual discontinuation of the study drug. See Section 9.2.4 and Section 9.2.5 for procedures at the safety follow-up visits.

9.2.9 Unscheduled Visits

An Unscheduled visit may be performed at any time during the study at the subject's request or as deemed necessary by the investigator. Unscheduled visits will be scheduled e.g., if pump rate adjustments become necessary (see Section 8.4.9.2), when the subject has tolerability problems or has to down titrate the investigational treatment. Subjects should be advised that if tolerability problems continue then they should contact their investigator who may then withdraw them from the study. Subjects that complete the study and have unresolved nodules/skin problems at the last safety follow up visit will continue to be followed as considered necessary by the investigator.

At a minimum, concomitant medication data, AEs, and the date and reason for the Unscheduled visit will be recorded at this visit. Infusion site assessments will be performed and all infusion site reactions will be reported as AESI (see Section 10.1.3), whether or not considered clinically significant by the investigator.

When a subject attends an Unscheduled Visit between the scheduled visits they should be instructed to attend their next visit according to the study schedule as planned.

9.2.10 Duration of Treatment

The planned duration of treatment is 12 months of infusion with ND0612 in this study. At the end of the 12-month treatment period, an optional extended treatment period can be chosen by the subjects for an additional 24 months. If the product is not available on the market at the end of the 36-month treatment period, an optional long-term treatment extension period can be chosen by the subjects up to Month 102.

10 SAFETY AND EFFICACY VARIABLES

The planned schedule of assessments is in Section 8.1.2.

10.1 Safety Assessments

10.1.1 Adverse Events

Adverse Event Definition

An AE is defined as any untoward medical occurrence in a clinical study subject administered a medicinal product which does not necessarily have a causal relationship with this treatment. An AE can therefore be any unfavorable and unintended sign (including an abnormal laboratory finding), symptom, or disease temporally associated with the use of a medicinal (investigational) product, whether or not it is related to the medicinal (investigational) product. This includes an exacerbation of pre-existing conditions or events, intercurrent illnesses, drug interaction or the significant worsening of the indication under investigation that is not recorded elsewhere in the eCRF under specific efficacy assessments. Anticipated fluctuations of pre-existing conditions, including the disease under study that do not represent a clinically significant exacerbation or worsening need not be considered AEs.

It is the responsibility of the investigator to document all AEs that occur during the study. AEs will be elicited by asking the subject a nonleading question, for example, "Have you experienced any new or changed symptoms since we last asked/since your last visit?" AEs should be reported in the appropriate section of the eCRF.

Assessment of Severity

Each AE will be assigned a category by the investigator as follows:

Mild:	An AE that is easily tolerated by the subject, causes minimal discomfort, and does not interfere with everyday activities.
Moderate:	An AE that is sufficiently discomforting to interfere with normal everyday activities; intervention may be needed.
Severe:	An AE that prevents normal everyday activities; treatment or other intervention usually needed.

If there is a change in severity of an AE, it must be recorded as a separate event.

Assessment of Causality

Every effort will be made by the investigator to assess the relationship of the AE, if any, to the study drug. Investigators should use their knowledge of the subject, the circumstances surrounding the event, and an evaluation of any potential alternative causes to determine whether or not an AE is considered to be related to the study drug. Causality should be assessed using the categories presented below:

- Related: Adverse event judged by the investigator as having a reasonable suspected causal relationship to the investigational medicinal product
- Unrelated: Adverse event judged by the investigator as NOT having a reasonable suspected causal relationship to the investigational medicinal product

Action Taken

The investigator will describe the action taken in the appropriate section of the eCRF, as follows:

Action Taken:

- None
- Study Drug Stopped
- Study Drug temporarily interrupted
- Concomitant medication
- Other

Action Taken with Study Treatment:

- Dose Increased
- Dose Not Changed
- Dose Reduced
- Drug Interrupted
- Drug Withdrawn
- Not Applicable
- Unknown

Recording and Follow-up of Adverse Events

Adverse events will be recorded from informed consent to the final safety follow-up visit or the Early termination visit (if applicable). Subjects should be followed up for 3 months after receiving the last dose of study drug, and any AEs that occur during this time should be reported according to the procedures outlined above.

The subject will be followed as part of this protocol for 3 months after the last dosing.

All investigators should follow up subjects with AEs until the event is resolved or until, in the opinion of the investigator, the event is stabilized or determined to be chronic.

Documentation and Reporting of Adverse Events

AEs should be reported and documented in accordance with the procedures outlined below. All AEs occurring during the study must be documented on the relevant eCRF pages. The following data should be documented for each AE:

- Description of the symptom event
- Classification of "serious" or "not serious"
- Severity
- Date of first occurrence and date of resolution (if applicable)
- Action taken
- Causal relationship
- Outcome of event (unknown, recovered, not yet recovered, recovered with sequelae, death [with date and cause reported])

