11.1.4 Primary Analyses

11.1.4.1 Methods of Analysis

Adverse events will be coded using the Medical Dictionary for Regulatory Activities (MedDRA). Adverse events will be grouped by system organ class (SOC) and preferred term (PT) and summarized by treatment regimen. Only treatment emergent AEs (TEAEs) will be summarized. TEAEs are defined as all AEs that start or worsen on or after the start of first study drug administration in the present study and before the start of the optional treatment extension (for the 1-year analysis). It is assumed that AEs that started in study ND0612H-006 will not be recorded on the case report form of the present study (unless the event in question worsened during the present study), as these

events will not be TEAEs in the present study. For subjects who do not participate in the optional treatment extension, events that start >28 days after the last dose of study medication will not be defined as TEAEs.

The summary tables will present the frequency and percentage of total subjects and number of events, by SOC and by PT.

For the summaries of AEs, subjects who experience the same AE (in terms of the MedDRA PT) more than once will only be counted once for that event in the number of subjects but all occurrences of the same event will be counted in the number of events. In addition, separate summaries will be provided for AEs by severity and relationship to study drug, as well as separate summaries for AEs leading to study drug discontinuation and SAEs.

In addition to the frequency counts and percentages, the AEs will be presented as annualized rates. The annualized rates will be calculated by the total number of reported AEs divided by the total exposure time, measured as the total subject years of exposure to the study medication.

The below listed summaries will be produced for the Safety Set. In general, all safety endpoints will be summarized using either summary statistics or frequency tabulations, as applicable to the type of data.

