3.2. Primary and Additional Measures and Endpoints

3.2.1. Primary Outcome Measures

The primary objective of the study is to assess the long-term safety (systemic and local) and tolerability of continuous SC infusion of ND0612 throughout the 12-month treatment period. Assessments, which constitute the primary endpoint of this study, will be based on AEs, with a focus on AE's of special Interest (AESI's) which will include Infusion Site Reactions (ISR's), Hypersensitivity and Polyneuropathy. VAS for pain assessment will also be used as primary measure. Tolerability will be assessed based on percentage of subjects completing 12 months of treatment in the trial, and the percentage of subjects who discontinued from the 12-month treatment period due to a TEAE.

The definitions and analyses of these safety endpoints are provided in Section 7 of this SAP

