7.3.1.1. ISR Analyses

- Summaries for total ISR's, both as number of events, event rates adjusted to exposure and patient counts and percentages will be provided.

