7.3.1.3. Polyneuropathy Analyses

- Summaries for total Number of Polyneuropathy cases (by SOC and PT), will be presented as number of events, event rates adjusted to exposure and patient counts and percentages.
- Time to onset of Polyneuropathy will be presented by Kaplan Meier figures. In these analyses, the patients who did not experience Polyneuropathy will be right censored at the time of the last visit.
- Time from onset of Polyneuropathy to resolution will be presented with descriptive statistics. Unresolved cases will be right censored at the last visit
- Summaries for total number of Polyneuropathy will be broken down by Outcomes (unknown, recovered, not yet recovered, recovered with sequelae and death) and will be presented as number of events, event rates adjusted to exposure and patient counts and percentages.

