7.3.4. Adverse Events

Adverse events will be coded using MedDRA. Adverse events will be grouped by SOC and preferred term (PT). Only treatment emergent adverse events will be summarized. Treatment Emergent Adverse Events (TEAEs) are defined as all AEs that start (or worsen) on or after the start of first study drug administration in this study and before the start of the optional treatment extension. It is assumed that AEs that started in study ND0612H-006 will not be recorded on the case report form of the present study (unless the event in question worsened during the present study), as these events will not be TEAEs in the present study. For patients who do not participate in the optional treatment extension, events that start >28 days after the last dose of study medication will not be defined as TEAEs. The summary tables will present the frequency and percentage of total subjects and number of events, by SOC and by PT.

For tables of incidence of AEs, subjects who experience the same AE (in terms of the MedDRA PT) more than once will only be counted once for that event in the number of subjects but all occurrences of the same event will be counted in the number of events.

Events with a missing start time, but with a start date equal to the date of first dose of study treatment after baseline will be considered treatment-emergent. If the AE start date is incomplete, it will be imputed as follows for the purpose of determining TEAE:

- If the start date is completely missing, the start date will be equal to the date of the first dose of study treatment. However, if the stop date is not missing and is before the date of the first dose of study treatment, then the stop date will be used instead.
- If the start day is missing, but the month and year are not missing and are equal to the month and year of the first study dose, then this event will be considered as TEAE.
- If the start day and month are missing, then the first day of the first month (January) will be used.

The original date and time will be shown on all listings of AEs. Listings will be provided for all AEs, serious AEs, AEs leading to study treatment discontinuation, AEs leading to dose adjustment/temporary withdrawal and deaths.

The following summaries will be provided:

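### Each severity change opens a new AE record and every record is counted, so one fluctuating infusion-site reaction inflates the primary event count and rate

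*Protocol*

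**What the plan says.** Three sets of rules combine here.

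- **Recording.** Under Assessment of Severity, Protocol 10.1.1 states: "If there is a change in severity of an AE, it must be recorded as a separate event". The rule is mandatory and not limited to worsening. The items to be documented for each AE, listed in the same section, include a date of first occurrence and, where there is one, a date of resolution. No item ties a record to a parent event.
- **Counting.** Protocol 11.1.4.1 says that "all occurrences of the same event will be counted in the number of events". SAP 7.3.4 agrees: a subject with a repeated preferred term (PT) "will only be counted once for that event in the number of subjects but all occurrences of the same event will be counted". For the rate, Protocol 11.1.4.1 says: "The annualized rates will be calculated by the total number of reported AEs divided by the total exposure time", with exposure in subject-years.
- **Primary status.** SAP 3.2.1 says: "Assessments, which constitute the primary endpoint of this study, will be based on AEs", with the emphasis on AEs of special interest, infusion-site reactions among them. For these reactions SAP 7.3.1.1 promises totals "both as number of events, event rates adjusted to exposure and patient counts and percentages will be provided". Protocol 11.1.4.1.2 matches it.

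Two further rules matter for the secondary effects. Treatment-emergent AEs (TEAEs) in SAP 7.3.4 "are defined as all AEs that start (or worsen) on or after the start of first study drug administration". In SAP 7.3.1.3, "Time from onset of Polyneuropathy to resolution will be presented with descriptive statistics", and SAP 7.3.1.2 plans the same for hypersensitivity. In both, unresolved cases are censored at the last visit.

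**The concern.** Read together, these rules make the event count depend partly on how often reactions occur and partly on how often someone re-grades them. There are many chances to re-grade. Protocol 10.1.3 has infusion sites assessed at every clinic visit, and every reaction is reported and graded whether or not it is clinically significant.

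The AE records also carry most of the local-safety evidence. Under SAP 7.3.3 the erythema, edema, Draize, nodule and hematoma data go to listings only. Apart from the pain VAS, summarised local safety therefore rests on AE reporting. In addition, Protocol 11.1.7 and SAP 5.4 rely on annualised rates to allow for incomplete follow-up, so the measure meant to handle dropout is the one that is distorted.

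**Working it through.** The plan gives no figure to reproduce. The analysis is descriptive, no formal sample size was calculated, and no AE rate is anticipated. The check applies the plan's own rules.

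**Step 1: one reaction.** A reaction graded mild, then moderate, then mild has two severity changes. Records = 1 + 2 = 3. It contributes 1 subject to the patient count for its PT and 3 to the event count and rate numerator.

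**Step 2: a population.** Let p be the share of reactions that change grade and k the number of changes in each of those. Then:

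- records = reactions × (1 + p*k)
- rate = records / subject-years
- inflation = 1 + p*k

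The documents give neither p nor k, so both are assumptions. For illustration, take the 210 subjects of Protocol 11.2, and assume one reaction each and 210 subject-years. The rate free of splitting is 210/210 = 1.00 per subject-year.

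| p | k | Records | Rate per subject-year | Inflation |
|---|---|---|---|---|
| 10% | 1 | 231 | 1.10 | 1.10 |
| 10% | 2 | 252 | 1.20 | 1.20 |
| 25% | 1 | 262.5 | 1.25 | 1.25 |
| 25% | 2 | 315 | 1.50 | 1.50 |
| 50% | 1 | 315 | 1.50 | 1.50 |
| 50% | 2 | 420 | 2.00 | 2.00 |

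The factor does not depend on exposure. With 157.5 subject-years (210 × 0.75) the unsplit rate is 1.333, and for p = 50%, k = 2 it becomes 2.667, again a factor of 2.00. Nor does it depend on the number of subjects or of reactions per subject.

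**Step 3: treatment-emergent status.** Take a moderate AE starting on Day -10 that becomes mild on Day 5. The first record is not a TEAE. The second must be opened under Protocol 10.1.1. If it is dated Day 5, it starts after first dose and literally qualifies. If the original onset of Day -10 is carried over, it does not. The documents do not say which date applies.

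**Step 4: time to resolution.** Take a 60-day event re-graded at days 20 and 40, with split records dated from the change. If each superseded record is closed at the re-grade, the data show three durations of 20 days. If superseded records are left open, they are censored at the last visit and can look longer than the event was. The direction of the error is therefore not determined.

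**The case against.** **Occurrences might mean clinical episodes.** This reading does not survive Protocol 10.1.1, which itself makes each re-grade a separate event. That section's exemption for expected fluctuation concerns pre-existing conditions, not reactions to the infusion.

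**Much of the primary analysis is untouched.** This stands. Each subject counts once per PT, so one should not infer that the percentage of subjects with an infusion-site reaction is inflated. Completion, discontinuation due to a TEAE and VAS pain do not count AE records, and time to first onset of an on-treatment event uses the first record.

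**An improving pre-treatment AE becomes a TEAE.** A reader might infer this as a fact, but the documents support it only conditionally. It needs the split record to be dated from the change, and the definition's mention of worsening suggests that improvement was not meant to qualify. The reach is also narrow. SAP 7.3.4 assumes that AEs begun in study ND0612H-006 are not re-recorded unless they worsen. That leaves mainly AEs from Cohort 2 screening, which in ND0612-naive subjects cannot be reactions to an ND0612 infusion.

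**Resolution times are biased short.** This too is tempting but not established, as Step 4 shows. No time-to-resolution analysis is planned for infusion-site reactions.

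**The over-count is conservative, and nothing is tested.** Both are true and limit the consequence. But an event rate published as a primary safety result should still count reactions.

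**The eCRF may already link records.** Possible. The SAP's authors reviewed the CRF, and it is not among the documents. What can be said is that neither the protocol nor the SAP describes a link or uses one.

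**Conclusion.** The point holds for event numbers and exposure-adjusted rates. Followed as written, the plan counts a fluctuating reaction more than once in a primary output. Splitting can only raise these figures. The size, 1.1 to 2.0, is arithmetic on assumed inputs (p = 10 to 50%, k = 1 to 2) and not an estimate for this trial.

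The effects on treatment-emergent status and on onset-to-resolution times for hypersensitivity and polyneuropathy are ambiguities to settle, because they turn on an unstated dating and closing convention. A smaller gap is that SAP 7.3.4 tabulates drug-related TEAEs by severity without a maximum-severity rule, so one subject could appear under several grades.

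Since the analysis is descriptive and subject-level incidence by PT is protected, this is something the SAP should correct, not a flaw that undermines the study.

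**What to change.** In SAP 7.3.1 and 7.3.4:

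1. Combine severity-change records of the same reaction into one episode, with onset from the first record, end and outcome from the last, and the maximum severity. Use episodes for event counts, rates and time to resolution.
2. Combine only records identified as the same reaction, either by an eCRF link or by matching verbatim term and site location with contiguous dates and a different severity grade. Never combine on PT and dates alone. Two sites are infused in parallel and locations change daily (Protocol 8.1.1 and 8.1.1.1), so distinct lesions with the same PT and touching dates are to be expected. The per-AE items in Protocol 10.1.1 do not name site location; where it is not captured and there is no link, leave the records separate.
3. State that a severity change in a pre-dose AE is treatment-emergent only if it is a worsening.
4. Keep the uncollapsed records in listings and report the uncollapsed counts as a sensitivity summary.

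The cost is a SAP rule and some programming. There is a small risk of merging distinct lesions, and reported event rates will be lower, by an amount that the sensitivity summary will show.

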10.1.1.1 Adverse Events of Special Interest

Adverse events of special interest (AESI) include the following:

- Infusion site reactions
- Cases of hypersensitivity (e.g., diffuse skin rash, anaphylaxis and angioedema).
- Polyneuropathy

A dermatology examination is mandatory for the following 2 cases:

- 1. Infusion site reactions reported as SAE leading to withdrawal
- 2. Infusion site reactions reported as SAE requiring additional medical/surgical treatment

Additionally, the Investigator may refer to a dermatologist any infusion site reactions reported as an SAE or AE. The skin lesions should be photographed before and after treatment, if feasible.

The dermatologist consultant will document any relevant information of the lesion including pictures of the lesions.

10.1.1.2 Serious Adverse Events

Serious Adverse Event Definition

An SAE is any untoward medical occurrence or effect that, at any dose,

- Results in death.
- Is life-threatening (an AE is life-threatening if the subject was at immediate risk of death from the event as it occurred, i.e., it does not include a reaction that might have caused death if it had occurred in a more serious form).
- Requires or prolongs inpatient hospitalization. (Complications occurring during hospitalization are AEs and are SAEs if they cause prolongation of the current hospitalization. Hospitalization for elective treatment of a pre-existing non-worsening condition is not, however, considered an AE. The details of such hospitalizations must be recorded on the medical history or physical examination page of the eCRF).
- Results in persistent or significant disability/incapacity. (An AE is incapacitating or disabling if it results in a substantial and/or permanent disruption of the subject's ability to carry out normal life functions).
- Results in a congenital anomaly/birth defect.

In addition, medical and scientific judgement is required to decide if prompt notification is required in situations other than those defined for SAEs above. This may include any event that the investigator regards as serious that did not strictly meet the criteria above but may have jeopardized the subject or required intervention to prevent 1 of the outcomes listed above, or that would suggest any significant hazard, contraindication, side effect, or precaution that may be associated with the use of the investigational product.

Reporting of Serious Adverse Events

Any SAE must be reported by the investigator if it occurs during the clinical study or within 28 days of receiving the study drug, whether or not the SAE is considered to be related to the investigational product. An SAE report consists of the SAE form, the AE form, and the concomitant medication form. A copy of these forms must be emailed **within 24 hrs** for the attention of the product safety scientist at:

Email: [contact]

E-mail is the preferred reporting tool. In addition, sending reports by fax is also possible via the Global SAE Fax Line: [name].

The investigator should not wait to receive additional information to document fully the event before notification of a SAE, though additional information may be requested.

Where applicable, information from relevant laboratory results, hospital case records, and autopsy reports should be obtained.

Instances of death, congenital abnormality, or an event that is of such clinical concern as to influence the overall assessment of safety, if brought to the attention of the investigator at any time after cessation of study drug administration and linked by the investigator to this study, should be reported to the study monitor.

NeuroDerm will be notified of reported SAEs by the Syneos Health Pharmacovigilance Group as per the safety management plan. The sponsor and/or Syneos Health will promptly notify all relevant investigators and the regulatory authorities of findings that could adversely affect the safety of subjects, impact on the conduct of the study or alter the EC/IRB approval/favorable opinion of the study. In addition, Syneos Health, on behalf of the sponsor, will expedite the reporting to all concerned investigators, to the ECs/IRBs, where required, and to the regulatory authorities of all adverse reactions that are both serious and unexpected.

Details of the procedures to be followed if a pregnancy occurs are provided in Section 8.3.4.

